3.9 Safety Analyses

All safety analyses will use the Safety Set unless otherwise specified.

Safety endpoints include the following:

- Adverse events
- Vital signs and weight
- Physical examination
- Clinical laboratory tests
- Urinalysis
- ECG
- Ophthalmology and ERG examinations
- Columbia Suicide Severity Rating Scale (C-SSRS)
- Thyroid panel

- Inflammatory panel
- Coagulation
- Complement
- Immunogenicity.

For the analysis that will be performed after all patients have completed their EOT assessment, AE tables will include events with onset date up to seven days after last dose. An additional summary table of events while on-study (“summary of all TEAEs by PT and SOC”) will be created including all AEs recorded, even if onset date is more than 7 days after last dose. Unless noted otherwise, denominators for all tables will be number of subjects in the SS.

For visit based safety endpoints including laboratory assessments and vital signs, the analyses will use analysis visit windows.

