2.6 Blinding

The SAP will be finalized prior to unblinding. The EOT analysis will be performed after all patients have completed the EOT assessments, the database is locked and treatment code is unblinded. All of the safety and efficacy outputs will be produced for this final analysis. However, at the end of the study after all of the patients completed their post-treatment evaluation period or enrolled into open label extension study, all data listings and applicable outputs will be updated.

For the purpose of pre-programming and data cleaning, PPD [REDACTED] and a firewalled data manager working at the CRO contracted to perform data management (PPD [REDACTED]) will have access to the post-baseline mNIS+7, NSC, Norfolk-QOL-DN, SF-36, PND, ECHO and body weight. All staff at PPD [REDACTED] will be blinded to treatment assignment. At PPD [REDACTED] a small team responsible for providing the DSMB unblinded summary statistics for efficacy endpoints were unblinded to treatment assignments. Details of the unblinded analysis of efficacy endpoints including safeguards to ensure study integrity are detailed in Section 5.2.

3 Analytical Plan

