 - The baseline laboratory assessment including PD will be defined as the average of all non-missing pre-dose assessments.

- The baseline for all other assessments will be defined as the last non-missing value prior to the first dose of Study Drug.
- For efficacy endpoints except for BMI and mBMI:
 - The efficacy on-treatment period spans the time during which the study treatment is administered until 52 days after the last dose of medication.
 - The efficacy post-treatment period starts on the day after the efficacy on-treatment period and ends on the day of the patients's last contact date within the study.
- For BMI, mBMI and PD endpoints:
 - The on-treatment period spans the time during which the study treatment is administered until 28 days after the last dose of medication.
 - The on-post-treatment period starts on the day after the on-treatment period and ends on the day of the patient's last contact date within the study.
- For safety endpoints except ERG:
 - The safety on-treatment period spans the time during which the study treatment is administered until 7 days after the last dose of medication.
 - The safety post-treatment period starts on the day after the safety treatment period and ends on the day of the patient's last contact date within the study.
 - The safety on-study period spans the time drug is first administered until the day of the patient's last contact date within the study.
- For ERG:
 - The on-treatment period spans the time during which the study treatment is administered until 28 days after the last dose of medication.
 - The post-treatment period starts on the day after the on-treatment period and ends on the day of the patient's last contact date within the study.
- The PK and Immunogenicity (IM) on-study period spans the time drug is administered until the day of the patient's last contact date within the study.
- Note: Assessments for mNIS+7, NSC, ERG, and ophthalmology done early in the treatment period that are used for baseline cannot also be used as an on-treatment assessment.
- Body mass index (BMI) will be computed using the formula:

$$\text{BMI} = (\text{weight in kilograms}) / [\text{height in cm} / 100]^2$$
- Modified BMI (mBMI) will be computed from BMI and serum albumin levels by:

$$\text{mBMI} = \text{BMI} * \text{serum albumin (g/L)}.$$

- Duration of study drug exposure will be derived as the difference between the date of the last dose of study drug and the date of the first dose plus one.

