3.2.1.4 Data Summary Plan

The table below details what data will be included in the summary and analysis output by endpoint type, and what output is planned for the EOT and what output will be updated for the EOS. Data summarized/analyzed at EOT will be based on data collected up to the date of the data cut. It is possible that the on-treatment set of data available at EOS will be different to the one that was available at EOT because data collected after the EOT data cut may slot into the on-treatment period. On-treatment output provided at the EOT will be updated at EOS if the data in the on-treatment period has changed from EOT. In select instances the data for a type of endpoint that is summarized or analyzed may not be consistent with the rules in the Table; such exceptions will be noted in this document. Note: assessments for mNIS+7, NSC, ERG, and ophthalmology done early in the treatment period that are used for baseline cannot also be used as an on-treatment assessment.

Endpoint type	Provide at EOT	Update at EOS	Comment/definition
Efficacy	-Listings -On-treatment summary/analysis tables -Post-treatment summary tables	-Listings -On-treatment summary/analysis tables -Post-treatment summary tables	-On-treatment: First dose date \leq Date of assessment \leq Last dose date + 52 days -Post-treatment: Date of assessment $>$ last dose date + 52 days -Visit defined by analysis visit window -The primary inference for mNIS+7 and Norfolk QOL-DN will be made at EOT, even if data slotted in the on-treatment period has changed by EOS
PD, BMI and mBMI, ERG	-Listings -On-treatment summary/analysis tables -Post-treatment summary tables	-Listings -On-treatment summary/analysis tables -Post-treatment summary tables	-On-treatment: First dose date \leq Date of assessment \leq Last dose date + 28 days -Post-treatment: Date of assessment $>$ last dose date + 28 days -Visit defined by analysis visit window
ECG, Lab, vital signs (including body weight),	-Listings -On-treatment summary tables -Post-treatment summary tables	-Listings -On-treatment summary tables -Post-treatment summary tables	-On-treatment: First dose date \leq Date of assessment \leq Last dose date + 7 days -Post-treatment: Date of assessment $>$ last dose date + 7 days -Visit defined by analysis visit window -Abnormal lab analyses described in Sections 3.9.4.1 to 3.9.4.3 include post-baseline data

Endpoint type	Provide at EOT	Update at EOS	Comment/definition

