			collected up to the day of the patient's last contact date within the study
AE	-Listings -On-treatment summary tables -On-study summary tables	-Listings -On-treatment summary tables -On-study summary tables	-On-treatment summary tables include TEAE with onset dates up to the last dose date + 7 days -On-study summary tables includes all TEAE in the study, including those with onset dates > 7 days after last dose
Concomitant/ Prior medications	-Listings -On-treatment summary tables -On-study summary table	-Listings -On-treatment summary tables -On-study summary table	-On-treatment summary tables include medications taken on or after the study drug first dose date and up to the study drug last dose date +7 days - On study summary tables include medications taken after the study drug first dose date - Medications taken before the first dose date will be considered prior.
Immunogenicity	-Listings -On-study summary/ analysis tables	-Listings -On-study summary/ analysis tables	-On-study summary/analysis tables include post-baseline data collected up to the day of the patient's last contact date within the study -Visit defined by analysis visit window
PK	-Listings -On-study summary/ analysis tables	-Listings -On-study summary/ analysis tables	-Summary/analysis tables include post-baseline data collected include data collected up to the day of the patient's last contact date within the study -PK parameters will be derived based data collected up to the patient's last contact date within the study -PK concentration will be summarized based on nominal scheduled visits -All PK parameters will be recalculated using all available data at EOS

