3.9.2 Adverse Events

Treatment-emergent adverse events (TEAEs) are defined as adverse events that first occurred or worsened after the first dose of Study Drug. An AE with a completely missing start date will be assumed to be treatment emergent. Adverse events will be coded using Medical Dictionary for Regulatory Activities (MedDRA). The final version used will be designated in the clinical study report. For each TEAE, the severity level of the event (mild, moderate, or severe) will be determined by physician opinion. If the maximum severity of the adverse event is greater than the baseline severity, or if the onset date/time is the same as or after the date/time of the first dose of Study Drug, then the event is considered to be treatment emergent.

In the situation where change in severity (but no change in seriousness) occurs for an adverse event, study sites are instructed to enter an end date and start a new record for the adverse event. In the new record, the changed severity is to be recorded and the start date will be set to be the end date of the previous record. Data linking those records are collected in the database. Consider three scenarios:

- The first AE record occurs prior to the first dose, the second AE record occurs on or after the first dose, and the severity increases: Only the second record will be counted as treatment-emergent.
- The first AE record occurs prior to the first dose, the second AE record occurs on or after the first dose, and the severity decreases: Neither record will be counted as treatment-emergent.
- Both records occur on or after the first dose: If the AE severity on the second record is worse than the severity on the first record, then count both records as treatment-emergent. But, if the severity improves, then only count the first record as treatment-emergent.

Of note, when counting the total number of treatment-emergent events, events linked through change in severity will still be counted as separate events.

The following categories of AEs will be summarized by treatment group: all TEAEs; TEAEs leading to early discontinuation from Study Drug or from study; and serious adverse events. The percentages of patients reporting the adverse event will be summarized by MedDRA System Organ Class (SOC) and Preferred Term (PT), sorted by SOC alphabetically and then by decreasing frequency of PT within SOC.

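### SAP 3.9, read literally, cuts all EOT adverse-event tables but one at 7 days after last dose; this conflicts with Protocol 10.5.2 and sits poorly with SAP 3.2.1.4 and 3.9.2, so the window of each table must be stated

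*SAP*

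**What the plan says.** SAP 3.9 states that, for the analysis run once all patients have had their EOT assessment, "AE tables will include events with onset date up to seven days after last dose". It adds one table without that limit, the on-study summary of all TEAEs by preferred term and system organ class.

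SAP 3.2.1.1 defines the matching period: "The safety on-treatment period spans the time during which the study treatment is administered until 7 days after the last dose of medication". The Data Summary Plan (SAP 3.2.1.4) repeats the rule for one family of tables: "On-treatment summary tables include TEAE with onset dates up to the last dose date + 7 days". It then plans a second family, at both EOT and EOS: "On-study summary tables includes all TEAE in the study, including those with onset dates > 7 days after last dose". It does not say which outputs belong to which family.

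SAP 3.9.2 defines a TEAE by its start relative to the first dose and gives no end date. It names the tables to be made: all TEAEs, "TEAEs leading to early discontinuation from Study Drug or from study; and serious adverse events", related TEAEs, maximum severity, AEs of special interest and other AEs of interest. It lists TEAEs in the safety treatment period as a separate item. For the AEs of special interest and the other AEs of interest it plans risk differences with 95% confidence intervals. Thrombocytopenia is in the first group (3.9.2.1) and haemorrhage in the second (3.9.2.2). None of these tables is given a window of its own.

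Protocol 10.5.2 summarises TEAEs and SAEs by organ class, preferred term, relationship and severity, with no upper limit on onset.

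**The concern.** If SAP 3.9 governs, the only on-study AE table does not separate out serious events, grade severity, group AEs of special interest or bleeds, or give a between-arm comparison. A bleed first dated on day 10 after the last dose would be one line in a preferred-term table, outside the haemorrhage table and its risk difference. The discontinuation table has the same difficulty: it covers withdrawal from the study, which can follow an event that begins in post-treatment follow-up.

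The choice of window matters in this trial. Amendment 9 was prompted by a third case of severe thrombocytopenia; one of the two earlier cases included a fatal intracranial bleed. Protocol 8.5.4 requires weekly platelet counts for at least 6 weeks after the last dose. The SAP itself runs the laboratory side further: "Abnormal lab analyses described in Sections 3.9.4.1 to 3.9.4.3 include post-baseline data" up to the patient's last contact. One patient's platelet nadir could therefore be counted while the associated bleed is not in the haemorrhage table.

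Elsewhere the SAP marks departures from the protocol (tertiary endpoints in the Per-Protocol Set, retinol as a safety endpoint). It does not mark this one.

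**Working it through.** The documents give no late-event count, so there is no planned figure to reproduce. The check is of text, then of days, then of scale.

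**1. Texts side by side**

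| Place | What it implies for events after day 7 |
|---|---|
| SAP 3.9 | Out of all EOT AE tables except one |
| SAP 3.2.1.4 | In the on-study tables (plural), EOT and EOS, contents not named |
| SAP 3.9.2, TEAE definition | No end date |
| SAP 3.9.2, separate safety-treatment-period summary | Suggests the other TEAE tables are not cut; not stated |
| Protocol 10.5.2 | In the TEAE and SAE summaries |

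Two programmers could build different SAE, special-interest and haemorrhage tables from this SAP, each with text to support the choice.

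**2. Days outside the window**

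Inputs: Week 65 dosing visit Day 449, Week 66 Day 456, Week 71 Day 491, Week 91 Day 631 (Protocol Appendix A). AE collection ends at Week 91, or at the EOT efficacy assessment for patients entering the open-label extension (OLE) (Protocol 9.4.1, 9.4.2).

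- Completer not entering the OLE: 631 − 449 = 182 days (26 weeks) after last dose. Outside the window: 182 − 7 = 175 days, or 175/182 = 96%.
- Mandatory platelet monitoring: 491 − 449 = 42 days. Outside: 42 − 7 = 35 days, or 35/42 = 83%.
- OLE entrant: 456 − 449 = 7 days, at most 14 under Protocol 6.1.3. Little or nothing is lost.

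These spans assume a last dose on Day 449. Early terminators have an earlier last dose and also enter post-treatment follow-up, so they can lose events too; their span is not fixed by the schedule.

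**3. Scale of a risk difference**

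Input: 90 active and 45 placebo (Protocol 3.3). For each patient whose only qualifying event is dated after day 7:

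- active: 1/90 = 1.1 points; five patients, 5/90 = 5.6 points
- placebo: 1/45 = 2.2 points; five patients, 5/45 = 11.1 points

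For comparison, the 95% half-width is 1.96 × √[p(1−p)/90 + p(1−p)/45], with an assumed common proportion p:

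| p (assumed) | Standard error | Half-width, points |
|---|---|---|
| 0.05 | 0.0398 | 7.8 |
| 0.10 | 0.0548 | 10.7 |
| 0.20 | 0.0730 | 14.3 |

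**4. Illustration with assumed counts**

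Start from 9/90 against 2/45 inside the window: 10.0% − 4.4% = 5.6 points (95% CI −3.1 to 14.2).

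| Late active patients added | Difference, points | 95% CI |
|---|---|---|
| 1 | 6.7 | −2.2 to 15.5 |
| 3 | 8.9 | −0.4 to 18.1 |
| 5 | 11.1 | 1.5 to 20.7 |

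Late placebo patients would move it the other way: 9/90 against 3/45 is 10.0% − 6.7% = 3.3 points. With so few placebo events the Wald interval is rough; the table shows order of magnitude only.

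**The case against.** **The Data Summary Plan may already settle it.** It assigns data to outputs, lists on-study AE tables in the plural at both locks, and names them for update at EOS. That also answers most of the doubt raised by SAP 2.6, which says only that "all data listings and applicable outputs will be updated". This stands in part: it shows that the cut is not settled. It does not name an on-study SAE, special-interest or haemorrhage table, and SAP 3.9 names a different one.

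**Late events are still visible.** A reader might infer that serious late events disappear from the report. The documents do not support that. They remain in the all-TEAE table, in the listings (including one by preferred term) and, for deaths and SAEs, in the narratives of Protocol 10.5.2. Platelet, renal and hepatic abnormality tables run to last contact. What is at stake is the place of late events in the named tables and comparisons.

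**A 7-day comparison is defensible.** Collection stops at the EOT assessment for OLE entrants and runs to Week 91 for others, so on-study risk differences depend on a choice made after randomisation. This stands, and is why the 7-day version should be kept.

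**Escalating events.** An event that starts in the window can become serious or worse later, and a reader might infer that it should be placed by its first onset. The documents point the other way: Protocol 9.4.3.5 gives the SAE its own onset date, SAP 3.9.2 opens a new record for a severity change, and the 7-day rule runs on onset date. Redating would bring seriousness or severity from outside the window into on-treatment tables. Nor does "In the situation where change in severity (but no change in seriousness) occurs for an adverse event" show that AE and SAE records are unlinked: that text deals with severity only, and the Data Management Plan is not among the documents. On-study tables capture these escalations without any redating.

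**Conclusion.** The point holds as an inconsistency with a practical consequence. As SAP 3.9 is written, SAEs, AEs of special interest and haemorrhages first dated after day 7 can be missing from their named EOT tables and from the planned risk differences. That conflicts with Protocol 10.5.2 and fits poorly with SAP 3.2.1.4 and 3.9.2.

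The size is unknown. No event rates are given, so neither the number of patients nor the direction of any effect can be computed, and a bias in favour of either arm should not be inferred. Against the assumed half-widths of about 8 to 14 points, one such patient matters little and several in one arm would matter. The exposure lies mainly with early terminators and patients who do not enter the OLE.

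This should be corrected before unblinding. It does not touch the efficacy conclusions.

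**What to change.** Before unblinding, reconcile SAP 3.9, 3.2.1.4 and 3.9.2:

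- List every AE table with its window (7-day on-treatment, on-study, or both), at EOT and at EOS.
- Produce the SAE, maximum-severity, discontinuation, special-interest and other-AE-of-interest (including haemorrhage) tables on both bases: onset to 7 days after last dose, and onset to last contact. Update both at EOS, as SAP 3.2.1.4 already provides for AE tables.
- Give the risk differences with 95% confidence intervals for AEs of special interest and other AEs of interest on both bases. Footnote the on-study version with follow-up length by arm and by OLE entry.

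No new rule for dating or linking AE records is needed.

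Cost: a short text change and additional tables from data already collected. The drawback is that on-study comparisons mix unequal follow-up and may include late events unrelated to study drug; the 7-day tables alongside and the footnote deal with that.

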3.9.1 Imputation of Missing/Partial Dates for Adverse Event

The following imputation rules will be applied to impute AE start dates under conservative principles. If the month, year, and day are missing, the adverse event start date will be imputed as the treatment start date. If month and day are missing and year is available and is the same year as in treatment start date, the month and day from the treatment start date will be used to impute the missing month and day for the adverse event start date. Otherwise, missing month and day will be imputed as January 01. If day is missing and month and year is available and the month and year are the same month and year in treatment start date, the day from the treatment start date will be used to impute missing day for the adverse event start date. Otherwise, missing day will be imputed as 01.

3.9.2 Adverse Events

Treatment-emergent adverse events (TEAEs) are defined as adverse events that first occurred or worsened after the first dose of Study Drug. An AE with a completely missing start date will be assumed to be treatment emergent. Adverse events will be coded using Medical Dictionary for Regulatory Activities (MedDRA). The final version used will be designated in the clinical study report. For each TEAE, the severity level of the event (mild, moderate, or severe) will be determined by physician opinion. If the maximum severity of the adverse event is greater than the baseline severity, or if the onset date/time is the same as or after the date/time of the first dose of Study Drug, then the event is considered to be treatment emergent.

In the situation where change in severity (but no change in seriousness) occurs for an adverse event, study sites are instructed to enter an end date and start a new record for the adverse event. In the new record, the changed severity is to be recorded and the start date will be set to be the end date of the previous record. Data linking those records are collected in the database. Consider three scenarios:

- The first AE record occurs prior to the first dose, the second AE record occurs on or after the first dose, and the severity increases: Only the second record will be counted as treatment-emergent.
- The first AE record occurs prior to the first dose, the second AE record occurs on or after the first dose, and the severity decreases: Neither record will be counted as treatment-emergent.
- Both records occur on or after the first dose: If the AE severity on the second record is worse than the severity on the first record, then count both records as treatment-emergent. But, if the severity improves, then only count the first record as treatment-emergent.

Of note, when counting the total number of treatment-emergent events, events linked through change in severity will still be counted as separate events.

The following categories of AEs will be summarized by treatment group: all TEAEs; TEAEs leading to early discontinuation from Study Drug or from study; and serious adverse events. The percentages of patients reporting the adverse event will be summarized by MedDRA System Organ Class (SOC) and Preferred Term (PT), sorted by SOC alphabetically and then by decreasing frequency of PT within SOC.

Summaries of related TEAEs, TEAEs by maximum severity, TEAEs during the safety treatment period, and TEAEs grouped by time from first dose to event onset (< 6 months, ≥ 6 months to < 12 months, ≥ 12 months) will also be provided.

All TEAEs will be summarized for subgroups defined by the following variables: Age, Sex, Race, Region, CM-ECHO Set, V30M TTR mutation, previous treatment with Vyndaqel® or Diflunisal, disease stage. Results will not be provided for a variable if the overwhelming majority of patients are within one level of the subgroup. Non-TEAEs reported will be flagged in the all AE listing.

A listing will be provided stating which subjects reported each preferred term. Adverse events in the following categories will be summarized separately:

- Adverse events of special interest
- Other adverse events of interest

Summary tables of the number and percentage of subjects with these adverse events will be displayed split by AE category and treatment group. TEAEs of special interest and other TEAE of interest will also be summarized for patients in the CM-ECHO Set. Statistical comparison between treatment groups will be done for AEs of special interest and other AEs of interest using the risk difference (ISIS 420915 – Placebo) and associated 95% CI.

